4.2 Exclusion criteria

All patients

Patients fulfilling **any** of the following criteria are not eligible for inclusion in this study:

1. Use of other investigational drugs at the time of Screening, or within 30 days or 5 half-lives of Screening, whichever is longer; or longer if required by local regulations.
2. Known hypersensitivity to any constituents of the study drug, to murine, chimeric or human antibodies, or to drugs of similar chemical classes (e.g., IgG1 biologics). Also, known hypersensitivity to study drug premedication (paracetamol (or acetaminophen) and H1 receptor blocker).
3. Prior use in the 12 months prior to Screening of any B-cell depleting therapy e.g., rituximab or other anti-CD20 mAb, anti-CD22 mAb, anti-CD52 mAb (patients B cell levels should also have returned to normal, if results are not available, a FACS sample should be taken at screening to confirm).
4. Use of prednisone or other systemic steroids for conditions other than pemphigus vulgaris within the 1 month prior to Baseline.
5. Use of topical steroids (or other topical treatment for PV) within 2 weeks prior to Baseline.
6. Recent previous treatment with phototherapy, biological therapy, immunosuppressive agents such as azathioprine (unless it is used as SoC medications for PV treatment as per inclusion criteria # 5), dapsone, or methotrexate. The following washout period will be required for such patients to be eligible to participate in the trial:
 - 6 months washout prior to Screening for IVIg, plasmapheresis, immunoadsorption or i.v. or oral cyclophosphamide;
 - 3 months washout prior to Screening for etanercept, adalimumab, ustekinumab, infliximab or any other immunologically active biologic therapy;
 - 1 month washout prior to Screening for UVB/PUVA therapy, dapsone, methotrexate, and any systemic immunosuppressants or other systemic treatment for PV.

Note: If taking consistent stable dose(s) of allowable standard-of-care (SoC) medications, these are allowable if dose /regimen is maintained throughout the study (refer to [Section 4.1](#) inclusion criterion #5).

Decisions about management of previous treatments are left to the treating physician in line with the patients' choices, and should be conducted according to local standard of care best practice. The present protocol does not support stopping a medication if the sole purpose is to allow a patient to then become eligible to enter the study.

7. History of major organ or hematopoietic stem cell/marrow transplant.
8. Active viral, bacterial or other infections at the time of Screening or Baseline, or history of recurrent clinically significant infection or of recurrent bacterial infections with encapsulated organisms.

9. Evidence of active or latent tuberculosis (TB), or inadequately treated infection with TB, as defined by the following:
 - A positive QuantiFERON® TB-Gold test at Screening or in the 6 months prior to ScreeningOR
 - A chest radiograph positive for active TB infection at Screening or in the 6 months prior to Screening
 - History of either untreated or inadequately treated latent or active TB infection
 - If a patient has previously received an adequate course of therapy for either latent or active TB infection (according to local standard of care or country guidelines), this is to be documented prior to dosing with study drug.
 - Receiving current therapy for active TB infection
 - If receiving treatment for latent TB infection, a patient may not be excluded, and can potentially be recruited but only with prior approval of the sponsor (in consideration of country incidence rates of multi-drug resistant TB, etc.)
10. Recent vaccination with live/attenuated vaccine within a 2 month period prior to Screening.
11. Current signs or symptoms of severe, progressive, or uncontrolled renal, hepatic, hematological, gastrointestinal, endocrine, pulmonary, cardiac, neurologic, cerebral, psychiatric, or other disease which would make the patient unsuitable for the trial.
12. Significant illness within two 2 weeks prior to initial dosing.
13. History of primary or secondary immunodeficiency, including a positive HIV (ELISA and Western blot) test result.
14. Presence of any malignancy of any organ system that has been under active treatment (e.g., radiation therapy or chemotherapy) within the 2 years prior to Baseline or is anticipated to require treatment during the study period (including follow-up) with the exception of patients with removal of uncomplicated basal cell carcinoma or cutaneous squamous cell carcinoma, who may take part in the study.
15. Screening CBC laboratory values as follows:
 - Hemoglobin <10.0 g/dL
 - White blood cell count <3,000/ μ L
 - Platelets <100,000/ μ L
 - Absolute neutrophil count \leq 1,500/ μ L
16. A positive Hepatitis B surface antigen or Hepatitis C test result at Screening.
17. History of alcohol or substance abuse unless in full remission for greater than 12 months prior to Screening.
18. Pregnant or nursing (lactating) women, where pregnancy is defined as the state of a female after conception and until the termination of gestation, confirmed by a positive hCG laboratory test.

19. Women of child-bearing potential, defined as all women physiologically capable of becoming pregnant, unless they are using highly effective methods of contraception during dosing and for 4 months following study treatment. **Highly effective contraception methods include:**

- Total abstinence (when this is in line with the preferred and usual lifestyle of the patient. Periodic abstinence (e.g., calendar, ovulation, symptothermal, post-ovulation methods) and withdrawal are not acceptable methods of contraception.
- Female sterilization (have had surgical bilateral oophorectomy with or without hysterectomy) or tubal ligation at least six weeks before taking study treatment. In case of oophorectomy alone, only when the reproductive status of the woman has been confirmed by follow up hormone level assessment.
- Male sterilization (at least 6 months prior to screening). For female patients on the study the vasectomized male partner should be the sole partner for that patient.
- Combination of any two of the following (a+b or a+c, or b+c):
 - a. Use of oral, injected or implanted hormonal methods of contraception or other forms of hormonal contraception that have comparable efficacy (failure rate <1%), for example hormone vaginal ring or transdermal hormone contraception;
 - b. Placement of an intrauterine device (IUD) or intrauterine system (IUS);
 - c. Barrier methods of contraception: Condom or Occlusive cap (diaphragm or cervical/vault caps which are NOT made of latex) with spermicid, or condom only if in Germany. Note: in Germany, the concomitant use of a condom with spermicidal foam/gel/film/cream/vaginal suppository is not recommended.

In case of use of oral contraception, women should have been stable on the same pill for a minimum of 3 months before taking study treatment.

Women are considered post-menopausal and not of child bearing potential if they have had 12 months of natural (spontaneous) amenorrhea with an appropriate clinical profile (e.g. age appropriate, history of vasomotor symptoms) or have had surgical bilateral oophorectomy (with or without hysterectomy) or tubal ligation at least six weeks ago. In the case of oophorectomy alone, only when the reproductive status of the woman has been confirmed by follow up hormone level assessment is she considered not of child bearing potential.

20. Donation or loss of 400 ml or more of blood within eight (8) weeks prior to initial dosing, or longer if required by local regulation.
21. Have any other severe acute or chronic medical or psychiatric condition (e.g., severe mental impairment) or clinical laboratory abnormalities that may increase the risk associated with study participation/treatment or may interfere with interpretation of study results and, in the investigator's opinion, would make the patient inappropriate for entry into this study.

Open-label patients (i.e. for placebo-treated patients)

1. CBC laboratory values as follows:

- Hemoglobin <10.0 g/dL
- White blood cell count <3,000/ μ L
- Platelets <100,000/ μ L
- Absolute neutrophil count \leq 1,500/ μ L

No additional exclusions may be applied by the investigator, in order to ensure that the study population will be representative of all eligible patients.

5 Treatment

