3. Assessments to be conducted locally at Screening to confirm presence of pemphigus vulgaris (PV) only where not previously performed and documented as part of the patient's regular medical care.
4. Vital signs: Sitting blood pressure and heart rate measurement required at all visits, plus standing measurements only at Screening and Baseline. During study drug administration, blood pressure and heart rate should be obtained every 30 minutes.
5. For women, serum pregnancy testing (human chorionic gonadotropin, hCG) is required screening and end of study regardless of reported reproductive/menopausal status. Urine pregnancy test will be performed at Baseline (Day 1) and every post-dose visit from Week 3 onwards, and may be conducted in addition at the discretion of the investigator or may be required more frequently by local practices, if a menstrual cycle is missed, or if potential pregnancy is otherwise suspected.
6. For postmenopausal women, FSH conducted at Screening to assist in confirming menopausal status.
7. Administration: VAY736 infusion over 1-2 hours following premedication with paracetamol (or acetaminophen) and a H1 receptor blocker.
- 8.
9. Commercially Confidential Information
- 10.
- 11.
12. PK samples on Day 1 to be taken (1) pre-dose, (2) at the end of infusion when the indwelling line is empty and (3) 24 h post-dose (start of infusion: \pm 2 h).
13. Assessment completed by the investigator.
14. Assessment completed by the patient.
15. Commercially Confidential Information
16. At the selected sites (refer to footnote 15) this sample will be collected after Week 12 if the IGA score increases by at least 1 compared to the previous visit in patients that have previously reached disease control.
17. At Week 24 the blind will be broken and patients who were on placebo will be offered the opportunity to receive open label VAY736 administration at Week 25, and will follow the same visit pattern as if re-starting from Day 1. Refer to [Section 5.5.8](#) for unblinding prior to Week 24.

18. Serious adverse events are reportable from time of signing informed consent until 30 days after patient has stopped study participation. During the second part of the long-term safety follow-up (from Week 76), only AEs related to VAY736 and/or to infection, potential malignant events and neutropenia will be recorded.

19.

Commercially Confidential Information

20.

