After 24 weeks in the study, at the Week 24 visit (or before in case of early withdrawal from the double-blind period that meets certain conditions – see [Section 5.5.8](#)), patients' treatment will be unblinded. When the blind is broken and a patient was assigned to placebo during the double blind period, such a patient will be offered the option to receive open label VAY736 administration from approximately one week after the Week 24 visit, and will follow the same visit pattern as if re-starting from Day 1. Patients will be assigned a new patient number for the open-label treatment. Patients joining the open label part of the study have to satisfy inclusion for active disease and safety labs as mentioned in [Section 4](#), within 2 weeks of their prior Week 24 visit. The dose of VAY736 administered will be 3 mg/kg if a patient reaches Week 24 prior

to the study safety review or 10 mg/kg if dosed after a favorable safety review by the DMC. If a patient prefers not to receive open label active treatment, they are to return within 4 weeks for their EoS visit.

For logistical reasons, it may be necessary for patients to come to the site or a hotel the evening before their scheduled assessment visit, or remain at the site following the visit (e.g. transport restrictions, long travel times from home to site). In these instances, the patients would be hospitalized at the site, but this would not be considered as an SAE.

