5.5.8 Rescue medication

Except the patient's Standard of Care treatment (SoC; oral corticosteroid +/- adjuvant therapy) described in [Section 5.5.5](#), no additional rescue medication is allowed; however, adjustment to a patient's SoC is allowable, with certain conditions, for a patient to remain on study.

During the Double-blind period (Weeks 0 to 24), adjustment of SoC is limited to one (1) increase (either corticosteroid or adjuvant therapy alone or both on the same day) in the first 24 weeks if the IGA score worsens by 1 point or more. With one increase, a patient can continue on the study without change to the study visit schedule.

If a patient has already had an increase in oral corticosteroid or in adjuvant immunosuppressive drugs (azathioprine or mycophenolate mofetil) and is still experiencing a disease flare up that in the Investigator's opinion requires intervention (e.g., IGA score worsens by a further 1 point or more from the prior SoC increase timepoint), then depending on when this second increase of SoC happens the patient should follow the schedule below:

- Second increase in SoC up to & including Week 12 – Patient to return and complete visits up to & including the Week 12 visit. Treatment to be unblinded early at the Week 12 visit.
- Second increase in SoC after Week 12 – Patient to return and skip forward to complete the Week 24 visit assessments. Treatment to be unblinded early (at the time of SoC increase or at the Week 24 visit).

Following this early unblinding, a patient on placebo is to be offered the opportunity of open label VAY736, whereas a patient on VAY736 would enter the long-term follow-up period (from Week 32 onwards). Similarly, if a patient previously on placebo prefers not to receive open label active treatment, they are to return within 4 weeks for their EoS visit

Commercially Confidential Information

If more than two increases of SoC treatment are required in an aim to control a patient's disease symptoms, such a patient will already have been withdrawn from the double-blind period and skipped forward to be monitored in the long-term follow up period following the second increase in SoC. Such patients would already have had their treatment unblinded after the second increase. These patients should continue to return for the visits/assessments in the long-term follow up period (from Week 32 onwards).

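### Open-label VAY736 entry: the live-vaccine exclusion, and less clearly the hepatitis and TB test exclusions, stay dated to a Screening about 25 to 29 weeks before a Week 25 infusion

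*Protocol*

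**What the plan says.** **Open-label entry.** Protocol 4.2 ends with a separate list for placebo patients entering the open-label part. It has one item: limits for hemoglobin, white cells, platelets and neutrophils. The section then closes with "No additional exclusions may be applied by the investigator, in order to ensure that the study population will be representative of all eligible patients". The synopsis carries the same single item. Section 3.1 agrees: "Patients joining the open label part of the study have to satisfy inclusion for active disease and safety labs as mentioned in" Section 4, within two weeks of the Week 24 visit.

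**Timing.** Footnote 17 of the assessment schedule says "patients who were on placebo will be offered the opportunity to receive open label VAY736 administration at Week 25". Section 5.5.8 adds an earlier route after a second increase in standard of care: "Following this early unblinding, a patient on placebo is to be offered the opportunity of open label VAY736". In the usual case the patient "will follow the same visit pattern as if re-starting from Day 1" (3.1).

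**The 'All patients' exclusions in 4.2.** Several safety criteria carry a date:
- 8: "Active viral, bacterial or other infections at the time of Screening or Baseline"
- 9: test results, for example "A chest radiograph positive for active TB infection at Screening or in the 6 months prior to Screening"
- 10: "Recent vaccination with live/attenuated vaccine within a 2 month period prior to Screening"
- 12: significant illness in the two weeks before initial dosing
- 16: a positive hepatitis B or C result at Screening

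**The concern.** For a placebo patient, the open-label infusion is the first real exposure to VAY736. Section 3.6 names increased infection as a theoretical risk of the drug, on top of other immunosuppressants. Section 5.2 sets the open-label dose at 10 mg/kg once the safety review is complete. A patient unblinded early has needed a second increase in standard of care, so may be more immunosuppressed than at first entry.

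The conditions screened out before the blinded infusion matter at least as much at this point. If the criteria still look back from the first Screening, a condition that arose during the double-blind period can go unasked. The live vaccine is the plainest example. Section 3.6.1.2 recommends completing planned immunizations before exposure to VAY736, and a placebo patient's exposure is still to come at unblinding.

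**Working it through.** The protocol gives no figure to reproduce. The check is a comparison of dates, then simple arithmetic on elapsed time.

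**Step 1: was any Screening-dated criterion restated for open label?** Yes. Exclusion 15 sets the blood-count limits at Screening, and the open-label list repeats them without the Screening date. Standard-of-care stability is also restated in 4.1. Exclusions 10, 16 and the dated tests in 9 are not restated.

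**Step 2: does the restart supply a new date?** Footnote 1 of the schedule defines Day 1 as Baseline/Dosing, and footnote 2 places a review of eligibility criteria there before dosing. Sections 4.1 and 5.2 also call the open-label infusion day Day 1. No new Screening visit is named, and the schedule marks the hepatitis/HIV and TB tests in the Screening column only.

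| Exclusion | Dated to | New date if open-label Day 1 counts as Baseline and initial dosing? | Other visible cover |
|---|---|---|---|
| 8 infection | Screening or Baseline | Yes, plausibly | Recurrent-infection limb undated; 11 and 21 undated |
| 12 significant illness | Initial dosing | Yes, plausibly | 11 and 21 |
| 9 TB tests | Screening or up to 6 months earlier | No | Lead text, history and current-therapy limbs undated; best-practice precautions in 6.2 |
| 16 hepatitis | Screening | No | Discretionary re-test in 6.2, no stated consequence |
| 10 live vaccine | 2 months before Screening | No | None visible; not in the visible part of Table 5-3 |

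Exclusion 20 (blood loss) is dated to initial dosing and behaves like 12. Exclusion 13 (immunodeficiency, including HIV) has no date, and 14 (malignancy) has a limb covering the whole study period. Neither is counted as a gap.

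**Step 3: how old is the first Screening at the open-label infusion?** Inputs: Screening on Day -28 to -1, so 1 to 28 days before Day 1; Week 24 visit on Day 169, which is 168 days after Day 1; infusion about one week later (3.1).
- Day 1 to infusion: 168 + 7 = 175 days.
- Age of Screening: 175 + 1 = 176 to 175 + 28 = 203 days, or 25.1 to 29.0 weeks.
- With the 7-day visit window at Week 24: from 169 days (24.1 weeks) to 210 days (30.0 weeks).
- Oldest accepted TB test, taking 6 months as 183 days: 203 + 183 = 386 days, about 55 weeks.

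For unblinding at Week 12, 5.5.8 gives no interval to the infusion. Assuming the same one-week gap, 84 + 7 = 91 days, so Screening is 92 to 119 days old (13 to 17 weeks). With no gap it is 85 to 112 days (12 to 16 weeks).

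The live-vaccine question thus covers only the two months ending 25 to 29 weeks before a Week 25 infusion.

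**Step 4: how many patients?** Six placebo patients are planned. At the overall ratio of 3:3:2, 32 × 2/8 = 8.

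**The case against.** The strongest reply is that 4.2 heads its 21 exclusions as applying to all patients, and the closing sentence only bars criteria from outside the protocol, as Section 4 already does. On that reading the undated exclusions 11 and 21 remain, and the Day 1 review can catch an unwell patient. Sections 6.5.1 and 6.5.2 add attention to infection at examination and regular monitoring, and 3.6 requires local prophylaxis. This largely stands for 8 and 12. A reader might infer that five safety exclusions (8, 9, 10, 12 and 16) simply lapse at open label, or that the investigator must infuse an infected patient. The documents do not support either inference: the infusion day is called Day 1, a criteria review sits on that day, and the undated exclusions still apply.

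For hepatitis, a re-test rule that refers to entry into an extension makes little sense unless the result bears on entry. That is fair as to intent, but the consequence is not written. For TB, the undated text and 6.2 give real cover. None of this reaches exclusion 10, whose date is Screening however Day 1 is read. Section 3.6.1.2 is general advice and does not direct anyone to give a live vaccine after unblinding.

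Redaction is a further limit. The Appendix 5 decision tree, schedule footnotes 19 and 20, the upper schedule rows and parts of 3.1, 5.5.8 and 5.5.10 cannot be seen and might hold entry rules. Section 5.5.8 describes Appendix 5 as settling the length of follow-up and the end of study, so it is a less likely place for them.

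**Conclusion.** The point holds as a minor safety clarification. In the visible text, exclusion 10 has no date relevant to a placebo patient's first VAY736 infusion, and exclusion 16 has a discretionary re-test without a stated consequence. The dated tests in 9 are old but partly covered. Exclusions 8 and 12 need only a sentence confirming the natural reading.

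The reach is 6 to 8 patients at most, all in an optional cohort. The documents do not say how many would be in such a state, and it may be none. The Week 12 comparison is not affected. The conclusion assumes that the redacted text holds no open-label entry rules. The elapsed times assume an infusion about one week after unblinding, which the protocol states for Week 24 but not for early unblinding.

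**What to change.** Amend 4.2 as follows, and align 3.1 and the synopsis:
- State that the 'All patients' safety exclusions continue to apply to open-label patients.
- Assess 8, 10 and 12 relative to the open-label Day 1.
- State that a positive hepatitis or HIV re-test done under 6.2, or newly identified TB, bars dosing.
- Limit the closing sentence to criteria beyond these.

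No mandatory repeat TB test is needed. The change is wording only and uses the criteria review already scheduled at Day 1. The downside is that a few of the 6 to 8 optional infusions may be delayed or refused, and a delay beyond the two-week window in 3.1 would mean repeating the PDAI and blood-count checks.

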5.1 Protocol requested treatment

5.1.1 Investigational treatment

The investigational drug, VAY736 will be packed by Novartis and supplied to the Investigator as open labeled bulk medication. The dosage form of the supplied drug is lyophilizate in vial and needs to be reconstituted with water for injection (USP or equivalent) and diluted in 5% dextrose infusion bag (USP or equivalent), both provided by the investigator's site. Please refer to [Table 5-1](#) for VAY736 formulation information.

The placebo control selected for this study is the 5% dextrose solution in the infusion bag.

Table 5-1 Study drug: VAY376

Name	VAY736	Placebo
Formulation	Powder for solution for infusion (lyophilizate in vial)	NA
Appearance before reconstitution	White lyophilized cake	NA
Appearance after reconstitution	Opalescent to clear, colorless solution	NA
Unit dose	150 mg per vial*	NA
Packaging	6 mL Type I glass vials	NA
Diluent for IV administration	Dextrose 5% in water (USP or equivalent) in 250 mL	Dextrose 5% in water (USP or equivalent) in 250 mL

* The vials contain a 20% overfill to allow a complete withdrawal of the labeled amount of VAY736

Clinical supplies are to be dispensed only in accordance with the specified study procedures.

An unblinded pharmacist or authorized designee is required to prepare the study drug. Instructions for storage and handling of VAY736 vials, and preparation of VAY736 and placebo infusions are described in the VAY736 Pharmacy Manual (or Dose Preparation Manual), provided as a separate document.

Of note, VAY736 vials require storage between 2-8°C.

